#### 5.0 Study Procedures

- 1. Recruitment
- 2. Consent
- 3. Enrollment of participants based on inclusion and exclusion criteria.
- 4. Guardians of enrolled participants will complete the baseline outcome measure

  Food Neophobia Scale for Children (FNSC) questionnaire consisting of 10 questions

  (Pliner, 1994). Guardians of participants will also complete an initial food list on the
  initial food log form including all foods that the participant currently tolerates. Included
  on the initial food log form will be a place for the caregiver to record the age and weight
  of the child. The weight of the child will be used to calculate the appropriate weight of
  the weighted blanket. The weighted blanket will not exceed 10% of the child's body
  weight. Weighted blankets are commercially available through the company yescool for
  children in weights of ten pounds, seven pounds, five pounds, and three pounds. Each
  participant will receive a weighted blanket that is approximately 10% of their body

weight but does not exceed 10% of their body weight. For example, if a child weighs 55 pounds, they will receive a five-pound weighted blanket. The initial food log form including the initial food list and weight of the child will be scanned and returned to the caregiver prior to the control period. The FNSC will be collected.

- 5. Participants will receive occupational therapy services treatment as usual without use of a weighted blanket for 1 month. During this period, participants will complete the S-Anxiety scale of the State-Trait Anxiety Inventory for Children (STAIC) three times per week upon sitting at the table prior to a meal (Spielberger, 1973). The S-Anxiety scale questionnaire will take about 8-12 minutes for a child to complete the first time and 5-8 minutes for repeated administrations. All forms and scales necessary for the control period will be provided to the caregivers prior to the control period of the study.
- 6. After the 1-month control period, caregivers will complete the FNSC and complete the second food list adding any new foods to the initial food log (Pliner, 1994). The principal investigator will collect the FNSC and the initial food log form at this time.

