- 7. Following the 1-month control period, participants and their guardians will receive a weighted blanket with verbal and written instructions for use and safety. The participants will continue usual care occupational therapy treatment during the treatment period. The caregivers will be provided with copies of the S-Anxiety scale of the STAIC, new food log, and a copy of the initial food log for reference (Spielberger, 1973). Participants will be instructed to use the weighted blanket for at least 5 minutes and no more than 15 minutes while participating in a quiet enjoyable activity prior to a meal with guardian supervision. Guardians will be responsible to keep the weighted blanket when not in use. Due to busy family schedules, it may not be possible to use

the blanket daily, therefore, the family will be asked to offer use of the blanket a minimum of 3 meals a week. On the days that the weighted blanket was used, the participant will complete the S-Anxiety scale of the STAIC at the table where they will consume the meal, following using the blanket and before eating the food (Spielberger, 1973). The guardians will be asked to record any new foods tried during the meal on the new food log along with the date each time the participant uses the weighted blanket.

- Upon completion of the 1-month treatment period, the guardians will complete the FNSC (Pliner, 1994). The principal investigator will collect the FNSC, new food log, and S-Anxiety scale of the STAIC at this time either through HIPAA protected email or in-person (Spielberger, 1973).
- 10. Once the study is completed the guardians will be gifted the weighted blanket to use as they deem appropriate

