#### 12.0 Biostatics and Subsidies

A statistical analysis using IBM SPSS Statistics (Version 28) predictive analytics software will be completed. The STAIC S-Anxiety scale mean score during the treatment period will be compared to the control period mean score using paired-samples t-tests (Spielberger,

1973). The control period mean score will be compared to the baseline. Similarly, the raw score from the FNSC during the treatment period and the raw control period score will be compared using paired-samples t-tests to understand if the children demonstrated a statistically significant change in food neophobia (Pliner, 1994). The control period raw score will be compared to baseline raw score using paired-samples t-tests. Nonparametric analysis will be used as necessary.

The average number of foods tried during the control period will be compared to baseline and the average number of new foods tried during the control period will be compared to the average number of new foods tried in the treatment period to understand if more foods were tried when using the weighted blanket. A paired-sample t-test will be completed to compare the control period to the treatment period. Nonparametric analysis will be used as necessary.

A weighted blanket will be provided to each of the participants of this study for their use following the study at no cost to the participant. The weighted blankets will be purchased by the principal investigator. This study is not funded by grants or subsidies.

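### New foods are recorded differently in the control and treatment months, so the Section 12.0 paired comparison of food counts mixes a change in recording with any blanket effect

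*Combined protocol and SAP*

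**What the plan says.** All recording steps are in Section 5.0 of the combined protocol and SAP.

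- **Baseline (step 4).** The guardian fills in an initial food log "including all foods that the participant currently tolerates". The form "will be scanned and returned to the caregiver prior to the control period".
- **Control month (step 6).** After the month, caregivers "complete the second food list adding any new foods to the initial food log". No date is asked for and no meals are singled out.
- **Treatment month (step 7).** Guardians are given a new food log, with a copy of the initial log for reference. They are to "record any new foods tried during the meal on the new food log along with the date each time the participant uses" the blanket. On frequency, "the family will be asked to offer use of the blanket a minimum of 3 meals a week".
- **End of treatment (unnumbered item after step 7).** "The principal investigator will collect the FNSC, new food log, and S-Anxiety scale of the STAIC at this time". No update of the full list is described.

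Section 12.0 takes the average number of new foods tried in each month as the measure: "A paired-sample t-test will be completed to compare the control period to the treatment period", with nonparametric analysis as necessary. It also says: "The average number of foods tried during the control period will be compared to baseline". Section 2.0 (Proposed Pilot Study) makes novel food consumption the second of the study's two questions and plans for 7 to 12 children.

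**The concern.** The recording method changes at the moment the blanket is introduced. Three things change together: when entries are requested (after the month, or at the meal), the form used (an addition to an existing list, or a dated log), and the meals covered (no restriction, or blanket meals only).

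Pairing removes stable differences between children. It does not remove a difference between months that applies to every child. A rank-based test does not remove it either, because the bias is in the counts themselves. Foods never written down cannot be recovered at analysis.

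The two main distortions act in opposite directions. Logging only blanket meals lowers the treatment count. An incomplete end-of-month control list lowers the control count and so flatters the blanket. The result could be a false benefit, a false harm or a hidden true effect, and the data would not show which.

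**Working it through.** **Is there a figure to reproduce?** No. The plan gives no significance level, power, expected food count or variance for this outcome. The calculation below shows only how sensitive the planned test is to unequal recording.

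**Inputs from the documents:** n = 7 (minimum) and n = 12 (maximum), and a paired t-test.

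**Assumed inputs:** two-sided 0.05; a mean of μ = 4 new foods per child per month; capture shares c (control month) and t (treatment month); blanket effect e as a rate ratio, with e = 1 meaning no effect. Counts are Poisson, with means μc and μte. Each range runs between two cases, one with no variation in rate between children and one with gamma variation (shape 2). There were 40,000 simulated trials per setting.

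**Size of the shift.** The expected paired difference is μ(te − c). Without between-child variation its variance is μ(te + c), so the shift in standard errors is μ|te − c|√n / √(μ(te + c)).

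- c = 1, t = 0.8, e = 1: difference 4 × (0.8 − 1) = −0.8 foods; SD √(4 × 1.8) = 2.68; shift 0.79 standard errors (n=7) or 1.03 (n=12).
- c = 1, t = 0.5, e = 1: difference −2.0 foods; SD √(4 × 1.5) = 2.45; shift 2.16 or 2.83.

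**False differences with no blanket effect (simulated, both directions of error added):**

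| Capture, one month against the other | n=7 | n=12 |
|---|---|---|
| Equal | 4–5% | about 5% |
| 90% against 100% | 5–6% | 7–8% |
| 80% against 100% | 8–10% | 14–16% |
| 50% against 100% | 33–45% | 65–74% |

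The totals are nearly the same whichever month is under-recorded; only the direction reverses. They depend on the assumed mean. At 50% against 100% they are 19–25% (n=7) or 38–45% (n=12) with a mean of 2 foods, and 54–73% or 89–96% with a mean of 8.

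**Masking.** Suppose the blanket truly gives 50% more foods (e = 1.5). With full capture in both months the test finds a benefit in 22–29% (n=7) or 45–52% (n=12) of trials. With 80% log capture against a full control list this falls to 7–9% or 12–13%. At two-thirds capture the effect cancels exactly, since 1.5 × 2/3 = 1.

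**Where might treatment capture lie?** Suppose new foods were spread evenly over three meals a day for four weeks, and only the minimum number of blanket meals took place. The log would then cover 3 × 4 = 12 of 21 × 4 = 84 meals, or 1/7. If nearly all new foods were offered at blanket meals, capture could exceed 90%. The documents do not settle where in this range the trial would fall.

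**The case against.** **Caregivers could fill in the control list as they go.** The form is returned to them before the month, and step 5 says the control-month forms are provided in advance. This stands in part. A reader might infer that the control count is pure end-of-month recall, and the documents do not go that far. Running entries are possible but not requested, and they would not settle the difference in meals covered.

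**New foods may cluster at blanket meals.** The product description (Section 6.0) presents the blanket as a calming step before new food is introduced. If so, the coverage gap shrinks and the bias from that source is small. But step 7 does not confine new foods to blanket meals, and clustering does not repair an incomplete control list.

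**The unit counted.** A reader might infer from the baseline list of tolerated foods that the two months count different things. Section 12.0 names new foods tried for both months, and step 6 says any new foods. What remains is form wording, and the forms are not available.

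**A missing end-of-treatment update.** A reader might infer that none is planned. The step numbers jump from 7 to 10, and the log forms and guardian handout are not in the documents. One can say only that the available text shows none.

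**The starting list for the treatment month.** Step 7 already supplies a copy of the initial log. It is natural to read this as including the foods added in step 6, but the text does not say so.

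**It is a small pilot.** That limits precision. It does not justify an avoidable bias of unknown sign.

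**Conclusion.** The concern holds as a mismatch in recording, and it should be fixed before data collection. As written, steps 6 and 7 produce counts by different methods, and Section 12.0 compares them as if they were alike. This affects the direct measure for one of the study's two questions. The anxiety and FNSC comparisons are untouched.

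Direction and size cannot be determined from the documents. A reader might infer that the plan favours the blanket, or that it works against it; the text supports neither. On the assumptions shown, the bias is small if the less complete month still captures 90% or more. It is material at 80%, and at 50% it can dominate the result. That the methods differ rests on the text alone. The percentages rest on assumed food rates and capture shares.

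**What to change.** **Preferred.** Use the same dated new-food log, with the same instructions, for all meals in both months. Start each month from the child's up-to-date list, and state that the copy given in step 7 includes the foods added in step 6. Count once each food tried that is not on that list. Mark blanket meals on the treatment-month log so that they can be described separately. Use these two counts in the Section 12.0 paired comparison, and report the mean paired difference with a 95% confidence interval.

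**Do not run a second log in the treatment month only.** Repeating the step 6 list while keeping a blanket-meal log in that month could leave recording unequal, because the log may prompt the list. With no blanket effect, assumed capture of 70% against 90% gives false differences in 9–11% (n=7) or 15–17% (n=12) of trials; 60% against 90% gives 15–20% or 30–34%.

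**If all-meal logging is too much for families.** Use the same log in both months at matched meals: the three weekly S-Anxiety meals in the control month and the blanket meals in the treatment month. Compare new foods per logged meal. This also removes the recording difference, but power depends on where new foods occur. For a true 50% increase, with the same number of meals logged in each month, it is about 20–27% (n=7) or 41–47% (n=12) if those meals capture 90% of new foods. It is only 6–8% or 9–11% if new foods are spread evenly over all meals (1/7 capture).

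**Cost.** Some extra caregiver logging in both months, which matters because step 7 itself mentions busy family schedules, and wording changes to steps 5–7 and Section 12.0. No extra participants, staff or visits are needed, and blanket use does not change.

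**Limit.** Equal recording does not remove any time trend from the fixed control-then-treatment order.

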### 4.0 Enrollment/Consenting Process

Children receiving occupational therapy services at Capital Area Speech and

Occupational Therapy to address feeding who have anxiety related to food will be offered enrollment via flyers and word of mouth. The first level of recruitment will include potential participants that have a patient relationship with the principal investigator or are receiving occupational therapy services from another occupational therapist at Capital Area Speech and Occupational Therapy. If 12 participants meeting the inclusion criteria cannot be recruited from Capital Area Speech and Occupational Therapy, the second level of recruitment will occur including other clinics in the Austin, Texas area who have given permission for flyers to be left in their waiting rooms. During the second level of recruitment, potential participants will contact the principal investigator for additional information regarding the study. A flyer will be available to potential participants with information about the study and principal investigator's contact information so that caregivers can ask questions. Potential study participants will only be provided additional information upon request regarding the study.

Recruitment will take place for 2 months and is anticipated to start April 2024 following IRB approval with researchers determining eligibility for the study based on inclusion and exclusion criteria. Participants and at least one guardian of each participant will be required to sign a consent form to affirm that they understand the purpose of this study, risks, and

requirements. To respect potential participant privacy, no information will be collected for research purposes prior to consent form completion. Also, no information of participants who withdraw from this study will be used. To consent to this study, potential participants will be provided with a consent form to review via email prior to signing it. Potential participants will be given an opportunity to speak with the investigator prior to signing the consent form.

No randomization will take place. There will be a control period consisting of usual care occupational therapy lasting 1 month prior to the treatment period lasting 1 month.

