#### 6.0 Sources of Research Material

Data for this study will be gathered by caregiver report via the Food Neophobia Scale for Children (FNSC) questionnaire consisting of 10 questions and parent interview to gather information about the age and weight of the child (Pliner, 1994). Participants will complete the State-Trait Anxiety Inventory for Children (STAIC) S-Anxiety scale consisting of 20 questions (Spielberger, 1973). The guardians will also complete a food log. All data collected from the assessments will be used for research purposes. No data from records will be reviewed for this study. In addition, any protocol deviations or unanticipated problems will be monitored.

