#### 8.0 Subject Safety

This study controls for risk as all use of weighted blanket will be under adult supervision and not during sleep. In addition, the participant can refuse the use of the weighted blanket at any

time during the study limiting any psychological risk or adverse events. Any adverse events will be reported immediately.

Prior to the start of the study, researcher will discuss best practices for weighted blanket use and guardians will be provided with a handout detailing the protocol and safety guidelines. The guardian will have the blanket in their possession and will only offer the blanket during times detailed in the protocol. All subjects will be given the opportunity to exit the program and withdraw consent at any time if they determine that they are no longer able to participate. The researcher will be available via HIPAA compliant email throughout the study to answer any questions that may arise and offer support. In person meetings will also be available upon request. All data collected throughout the program will be maintained on password protected emails and computers to reduce the risk for breach of privacy.

[name] will provide supervision as the faculty sponsor through a weekly check-in via email, phone or zoom meeting with the principal investigator. The principal investigator will notify the faculty sponsor immediately via email with any questions or concerns. The principal investigator will include the faculty sponsor on any emails with the participants to ensure appropriate monitoring. All information pertaining to this study will be available to [name].

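### Unmasked child and guardian reports go to an investigator who may be the child's therapist, so the paired tests would count a blanket-linked reporting shift as effect

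*Combined protocol and SAP*

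**What the plan says.** **Who reports.** In the treatment month of section 5.0, the "participant will complete the S-Anxiety scale of the STAIC at the table where they will consume the meal", after using the blanket and before eating. New foods come from the guardian: "The guardians will be asked to record any new foods tried during the meal on the new food log". The third outcome is also the guardian's: "Upon completion of the 1-month treatment period, the guardians will complete the FNSC". Section 6.0 (Sources of Research Material) excludes a check against records: "No data from records will be reviewed for this study".

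**Who receives the reports.** After the treatment month, "The principal investigator will collect the FNSC, new food log, and S-Anxiety scale of the STAIC at this time", by protected email or in person. After the control month the same investigator collects the FNSC and the initial food log, to which the guardian has added that month's new foods. The control-month S-Anxiety forms are not named in that step.

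**Who the investigator is.** Section 4.0: "The first level of recruitment will include potential participants that have a patient relationship with the principal investigator", or who are treated by another occupational therapist at the same clinic. Other clinics follow if 12 children cannot be found there. Section 12.0 adds: "The weighted blankets will be purchased by the principal investigator".

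**Design and analysis.** Section 4.0 rules out randomization, puts the control month first, and has families affirm at consent that they understand the study's purpose. Section 12.0 compares the treatment month with the control month by paired t-tests, with nonparametric analysis where needed.

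**Safeguards.** Section 2.0 states an intention to work without bias. Section 8.0 provides oversight: "The principal investigator will include the faculty sponsor on any emails with the participants to ensure appropriate monitoring". No visible passage plans a comparison blanket, masked collection, or any step that keeps individual answers from the treating therapist.

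**The concern.** A family that knows the study's purpose, has been given the blanket, and returns its answers to the child's own therapist has a reason to report that the blanket helped. That reason does not exist until the blanket is supplied, which happens after the control month. A shift in reporting of this kind would sit on one side of the paired comparison and be read as benefit.

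It could also act on S-Anxiety, FNSC and new foods together. Improvement on all three would look like mutual confirmation when it might share one source. Masking the family to a weighted blanket is hard. Keeping individual answers from the treating therapist is easy, and the plan does not do it.

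**Working it through.** The plan states no power, effect size, SD or significance level, so it has no figure of its own to reproduce.

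**Step 1: what cancels and what does not.** For child *i*, scored so that higher means better, let *g* be a general wish to please present in both months, *e* the extra reporting shift tied to the blanket, and *τ* the true effect. Then

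- control month = *g* + noise
- treatment month = *τ* + *g* + *e* + noise
- paired difference = *τ* + *e* + noise

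The same investigator collects forms in both months and usual therapy continues throughout, so *g* should largely drop out. The shift *e* does not. With *τ* = 0 the test is centred on *e*.

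**Step 2: inputs.**

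- *n* = 7 (minimum) and *n* = 12 (number requested): section 2.0, Proposed Pilot Study.
- Two-sided 5% level: assumed.
- *d* = *e* / SD of the paired differences = 0.3, 0.5, 0.8: assumed, to show a range. Nothing in the documents supports one value over another.

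**Step 3: false-significance rate with no true effect.** The rate is P(|T| > t(0.975, n−1)), where T is noncentral t with n−1 degrees of freedom and noncentrality *d*√n. The smallest observed standardized difference that reaches significance is 0.925 at n = 7 and 0.635 at n = 12, so the critical values are 0.925 × √7 = 2.45 and 0.635 × √12 = 2.20.

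| n | d | d√n | Rate |
|---|---|---|---|
| 7 | 0.3 | 0.3 × 2.646 = 0.79 | 10.3% |
| 7 | 0.5 | 0.5 × 2.646 = 1.32 | 20.1% |
| 7 | 0.8 | 0.8 × 2.646 = 2.12 | 42.8% |
| 12 | 0.3 | 0.3 × 3.464 = 1.04 | 15.8% |
| 12 | 0.5 | 0.5 × 3.464 = 1.73 | 35.3% |
| 12 | 0.8 | 0.8 × 3.464 = 2.77 | 71.4% |

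A simulation of 200,000 runs per setting gave 20.3% and 43.0% at n = 7, and 35.4% and 71.5% at n = 12, for *d* = 0.5 and 0.8.

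**Step 4: what the rates cover.** They apply to a shift from any cause. Write *d* = *d*(therapist) + *d*(expectation), the first part being pressure because the therapist will see the answers and the second being belief in the blanket. Changing who receives the forms acts on the first part only. The documents do not allow the split to be estimated, so no after-fix rate can be given. Recruiting toward 12 is no protection, because a larger sample makes a fixed bias more likely to reach significance.

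**The case against.** The strongest reply is that this is a small, single-group, open-label pilot, that reporting bias comes with that choice, and that changing who collects the forms leaves most of it in place. Families still know the purpose and the blanket. The child still fills in the form at the table after guardian-supervised use. Section 5.0 already brings the treatment-month forms to the investigator only when that month is over, so no passage has the investigator reading those answers while they are being given. All of this stands, and it limits what the fix can achieve. It does not remove the point: families can know when they answer that their therapist will read the form, and section 12.0 tests for significance whatever the study is called.

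Three stronger readings are tempting and are not supported:

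- *That the investigator treats some of the enrolled children.* Section 4.0 also admits patients of other therapists and, at a second level, of other clinics. The number treated by the investigator is not fixed and could be zero.
- *That families know who paid for the blanket.* Section 12.0 says who buys it. No visible passage says families are told, and the consent pages are not available. The argument does not need it.
- *That all pressure falls in the treatment month.* The investigator also collects control-month forms, so a general wish to please is present throughout. Only the blanket-linked part is one-sided.

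Faculty-sponsor oversight is not an answer as written, since it adds a reader without removing the therapist. The consent form or the handout mentioned in section 8.0 might say who sees the answers; neither can be checked here.

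**Conclusion.** The concern holds in a limited form. Every outcome is an unmasked report collected by an investigator who may be the child's therapist, and the paired tests would count blanket-linked reporting as effect. Its size is unknown. The ranges of 10-43% at n = 7 and 16-71% at n = 12 rest wholly on assumed shifts of 0.3 to 0.8 SD, an assumed two-sided 5% level, no true effect and a paired t-test.

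A reader might take the upper figures as error that sealed forms would prevent. They are not: the figures include expectation about the blanket, which no change in collection removes. The change is worth making because it is cheap and takes away one avoidable source of pressure. It does not make the comparison unbiased.

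**What to change.** In section 5.0, for both months, have families return the S-Anxiety forms, the FNSC and that period's food log marked only with study number, period and date. Use one of two routes:

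- envelopes kept sealed until the last family finishes; or
- return to the faculty sponsor, on paper or by the protected email already allowed, without copying the treating therapist.

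Only the child's age and weight and the baseline food list go to the investigator, for blanket sizing and reference. Record control-month new foods on a separate sheet instead of adding them to the initial log, and let the family keep a copy for reference in the treatment month. Name the control-month S-Anxiety forms in the collection step.

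Tell families at consent that their therapist will not see individual answers during the study. In section 12.0, state that expectation about the open-label blanket remains as a limitation, and that agreement across the three outcomes is therefore not independent confirmation of an effect.

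**Cost.** Envelopes, one extra sheet and a few sentences in the procedures, analysis section and consent information; no new staff, measure or visit. The investigator loses the chance to check completeness as forms arrive, so guardians should tick off the number of forms enclosed. Adverse events are reported separately under section 8.0, so safety reporting is unaffected.
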